### **7.2.3 Key Secondary Efficacy Endpoints Analysis**

For all key secondary endpoints, analyses will be performed in the Primary Population and in the SoC1 / Combination and SoC2 / Monotherapy Populations. As described previously, for the SoC1 / Combination and SoC2 / Monotherapy Populations, endpoints that refer to 52 weeks will in addition consider the 26 week timepoint (where applicable). Subgroup analyses will only be performed for the Primary Population and the SoC1 / Combination Population.

Initial analyses and subgroup analyses will be performed in only the mITT Analysis Set . Kaplan-Meier plots (where applicable) will only be produced for the mITT Set.

#### 7.2.3.1 Proportion of subjects with an absolute decline from baseline in % Predicted FVC of $\leq 10\%$ at Week 52

Spirometry data provided by an external central vendor (Clario/ERT) showing the calculated % Predicted FVC will be used to derive whether the subject showed an absolute decline  $\leq 10\%$  from baseline in predicted %FVC at Week 52.

The superiority of GB0139 3mg compared to Placebo will be tested for the proportion of subjects with an absolute decline  $\leq 10\%$  from baseline in predicted %FVC at week 52.

	Plus-Project Statistical Analysis Plan	
	Protocol Number: GALACTIC-1	Version: 1

The null hypothesis is:

H0: There is no difference in the proportion of subjects with an absolute decline  $\leq 10\%$  from baseline in predicted %FVC between GB0139 3mg and Plc.

The alternative hypothesis is:

Ha: There is a difference in the proportion of subjects with an absolute decline  $\leq 10\%$  from baseline in predicted %FVC between GB0139 3mg and Plc.

A logistic regression model will be fitted with treatment and baseline FVC (mL) included in the model. The Wald test will be used to test for differences between treatments. Odds ratios together with 90% and 95% confidence intervals will be used to quantify the effect of treatment, comparing GB0139 3mg to Placebo as the reference.

Subjects lost to follow-up prior to Week 52 are imputed to have absolute decline  $>10\%$  from baseline in predicted %FVC at Week 52.

The analysis will be repeated by subgroup (separately for each subgroup factor of interest, Section 7.1.1) by adding a fixed effect for the subgroup factor and adding a treatment by subgroup interaction term. The odds ratio between treatments will be assessed within each level of the subgroup.

Graphical displays will be provided of the mean ( $\pm$  SEM) observed predicted %FVC and mean change from baseline for each treatment group by visit.

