10.6 Withdrawal of Subjects from the Study

Subjects may withdraw for the following reasons:

- Lost to follow-up
- Study terminated by sponsor
- Withdrawal by subject
- Completed study
- Death
- Lung transplant
- Other (cause to be elaborated on in the subject's file)

All study procedures outlined for the withdrawal visit will be completed as specified in the Time and Events Table (Section 2.2). The primary reason for study drug discontinuation will be recorded on the eCRF.

Following the study withdrawal, no new information will be collected from the withdrawn subject and added to the existing data or any database.

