## 5.2 Definition of Analysis Visits

Assessments will be mapped to analysis visits for a variable as follows:

- Find the closest non-missing, within time-window (as per Table 1 below) result taken to the scheduled day as per the protocol schedule of assessments.
- If two assessments are equal distance either side of the scheduled day, then take the earlier result.

	Plus-Project Statistical Analysis Plan	
	Protocol Number: GALACTIC-1	Version: 1

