**Table 1: Study visits and analysis visit windows**

Visit	Description	Scheduled Day	Analysis window, Primary Population	Analysis window, SoC1 / Combination and SoC2 / Monotherapy Populations	Analysis Visit
V2	Baseline / Randomization	1	n/a	n/a	Baseline
V3	Visit 3 / Week 4	29	2-43	2-43	Week 4
V4	Visit 4 / Week 8	57	44-71	44-71	Week 8
V5	Visit 5 / Week 12	85	72-134	72-134	Week 12
V6	Visit 6 / Week 26	183	135-232	135-232	Week 26
V7	Visit 7 / Week 40	281	233-323	233-323	Week 40
V8 [a]	Visit 8 / Week 52	365	324-453	324-453	Week 52
V8 [b]	Visit 8 / Week 52	365	>=324	324-453	Week 52
FUV1 [a]	Follow-up 1 / Week 76	541	454-635	454-635	Week 76
FUV2 [a]	Follow-up 2 / Week 104	728	>=636	>=636	Week 104

[a] Subjects recruited under original design only.

[b] Subjects recruited under the updated design only.

Note: For the updated design, at the Follow up visit 7 days after the final study day visit only adverse events and concomitant medications are collected (does not require analysis visit windows).

All efficacy data will be considered for efficacy summary tables (i.e. summary tables by visit will include Week 76 and Week 104) but all data post Day 453 will be omitted from the efficacy analysis tables and any efficacy figures presented by visit will only be up to Week 52.

For time to event endpoints, Day 379 (Week 52 plus 2 weeks) will be considered the end of the period under consideration.

All safety data collected will be included in summaries.

In the proceeding sections of this SAP visit will mean analysis visit assignment per Table 1 unless stated otherwise.

	Plus-Project Statistical Analysis Plan	
	Protocol Number: GALACTIC-1	Version: 1

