### 7.1.2 Methods for Handling Missing Values

In general, missing data will not be imputed. Exceptions are detailed in the subsequent sections.

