### 7.2.2 Main Estimand and Analysis

The primary analysis will test for superiority of GB0139 3mg compared to Placebo (Plc) for the annual rate of decline in FVC in mL over 52 weeks in subjects not receiving pirfenidone or nintedanib at baseline in the mITT Set. The main estimand for the primary efficacy endpoint is as follows:

- Population: Primary Population, mITT set.
- Variable of interest: Change from baseline in FVC in mL over 52 weeks
- Intercurrent events:
  - Death: FVC attributed the lowest value recorded in the trial when a patient dies

	Plus-Project Statistical Analysis Plan	
	Protocol Number: GALACTIC-1	Version: 1

- Treatment Discontinuation: Analysis will include any FVC measurements after randomised treatment discontinuation
- Initiation of additional IPF therapy (nintedanib or pirfenidone): Analysis will include any FVC measurements after initiation of additional IPF therapy
- Summary measure: Comparison of slopes assessed through the treatment by time interaction.

The null hypothesis is:

$H_0$ : There is no difference in the annual rate of decline in FVC in mL between GB0139 3mg and Plc

The alternative hypothesis is:

$H_a$  : There is a difference in the annual rate of decline in FVC in mL between GB0139 3mg and Plc

A restricted maximum likelihood (REML) approach will be used, with a random coefficient regression (random slopes and intercepts) model fitted to test the hypotheses. The decrease in FVC is assumed to be linear within each subject over 52 weeks [5].

Baseline FVC and time will be fitted as continuous covariates. The treatment group and the interaction term for time by treatment group will be added as fixed effects. Random subject intercept and time effects will be fitted and will be assumed to be normally distributed with arbitrary covariance matrix. The within-subject errors will be assumed to be independent and normally distributed with mean zero and a common variance. The Kenward-Roger approximation will be used to estimate denominators degrees of freedom.

The statistical model will be as follows:

$$Y_{itk} = (\alpha + a_i + \tau_k) + \beta_f FVCb_i + (\gamma + \beta_3 T_3 + g_i) t + \varepsilon_{it}$$

where:

$Y_{itk}$  is the change from baseline measured for ith patient at time t (actual time) in treatment group k

$t$  is the time since randomization in years

$T_3 = 1$  if the subject is in the GB0139 3mg group, otherwise  $T_3 = 0$

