### 7.2.2.3 Supplementary Analysis

Supplementary analyses of the primary efficacy endpoint in the Primary Population will be performed as follows:

Supplementary Analysis	Analysis Set	Handling of intercurrent events		
		Death	Treatment discontinuation	Initiation of additional IPF therapy
1	mITT Set, Primary Population	FVC attributed lowest value recorded in the trial when a patient dies	Analysis will exclude all available FVC measurements after randomized treatment discontinuation	Analysis will exclude all available FVC measurements after initiation of additional IPF therapy
2	mITT Set, Primary Population	FVC attributed 0 when a patient dies	Analysis will include all available FVC measurements after randomized treatment discontinuation	Analysis will include all available FVC measurements after initiation of additional IPF therapy

	Plus-Project Statistical Analysis Plan	
	Protocol Number: GALACTIC-1	Version: 1

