### 7.2.3.3 Time to first hospitalization (respiratory related, including acute exacerbation of IPF)

The time to first hospitalization (respiratory related, including acute exacerbation of IPF) will be derived from the 'Exacerbation' and 'Adverse Events' eCRF.

If the subject was hospitalized and the AE linking to the hospitalization indicates that the PI/treating physician classed the AE as the result of an exacerbation of IPF then the hospitalization will be defined as being respiratory related, including acute exacerbation of IPF.

Other respiratory related causes will be defined as all AEs in the 'Respiratory, Thoracic and Mediastinal Disorders' System Organ Class (SOC), plus those AEs in the 'Infections and Infestations' SOC with preferred terms containing the character strings 'resp', 'bronch', 'covid-19' or 'pneumo', or the specific PTs as follows:

- Influenza
- Legionella infection
- Viral infection

If a subject was hospitalized (respiratory related, including acute exacerbation of IPF) prior to or on Day 379 (Week 52 plus 2 weeks) then the  $(\text{date of first such hospitalization} - \text{date of randomization} + 1) / 7$  will be derived as the time to first hospitalization (respiratory related, including acute exacerbation of IPF) in weeks.

If a subject does not require hospitalization (respiratory related, including acute exacerbation of IPF) prior to or on Day 379, they will be censored in the analysis. The following censoring rules will be applied:-

- If lost to follow-up (LTFU), a subject will be censored at the earliest of date of last contact and Day 379
- If a subject discontinued (and not lost to follow-up), they will be censored at the earlier of the date of study discontinuation and Day 379.
- Otherwise, censor at the earliest of last contact date or Day 379.

	Plus-Project Statistical Analysis Plan	
	Protocol Number: GALACTIC-1	Version: 1

The superiority of GB0139 3mg compared to Placebo will be tested for the time to first hospitalization (respiratory related, including acute exacerbation of IPF).

The null hypothesis is:

$H_0$  : There is no difference in the time to first hospitalization between GB0139 3mg and Plc

The alternative hypothesis is:

$H_a$ : There is a difference in the time to first hospitalization between GB0139 3mg and Plc

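### The ≤10% FVC responder endpoint has a failure rule for loss to follow-up but none for death; read literally, patients who die without a Week 52 FVC leave the analysis

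*SAP*

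**What the plan says.** The endpoint is the proportion of subjects whose absolute decline in % predicted FVC at Week 52 is no more than 10%. It is a key secondary endpoint, tested for superiority by logistic regression on treatment and baseline FVC (SAP 7.2.3.1).

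- **Rule for a missing outcome (SAP 7.2.3.1):** "Subjects lost to follow-up prior to Week 52 are imputed to have absolute decline" of more than 10%. No other reason for a missing value is named.
- **Default (SAP 7.1.2):** "In general, missing data will not be imputed", with exceptions given in later sections.
- **Week 52 value (SAP 5.2):** "Find the closest non-missing, within time-window (as per Table 1 below) result taken to the scheduled day". In Table 1 the Week 52 window opens at Day 324.
- **Death rule for the primary endpoint (SAP 7.2.2):** "Death: FVC attributed the lowest value recorded in the trial when a patient dies". SAP 7.2.2.3 and 7.2.2.4 also apply death rules, again only to the primary endpoint.
- **The ≤5% endpoint (SAP 7.2.4.1)** reuses the analysis of 7.2.3.1.

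Protocol 14.4.2.1 and the list of changes in SAP section 9 add no death rule for either responder endpoint.

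**The concern.** Under the written rules, a patient who cannot be traced counts as a failure, while a patient known to have died without an FVC from Day 324 on has no outcome and cannot enter the regression. The worse outcome is the one left out.

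This conflicts with three parts of the plan. Protocol 14.4.2 applies an intent-to-treat principle to all secondary endpoints. SAP 4.3 makes the mITT set, meaning all randomized and dosed subjects, the set for key secondary endpoints. The primary estimand treats death as a bad FVC outcome. At stake is whether the responder odds ratio compares the randomized arms or only the patients who lived long enough to be measured.

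**Working it through.** **Does any rule reach these patients?**

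1. *Is a death a loss to follow-up?* Protocol 10.6 ("Subjects may withdraw for the following reasons") lists loss to follow-up and death as separate entries. SAP 7.2.3.3 also keeps the category apart from other discontinuation: "If a subject discontinued (and not lost to follow-up), they will be censored".
2. *Does the primary death rule carry over?* It is written for the primary endpoint and assigns an FVC in mL. The responder endpoint uses the vendor's % predicted value.
3. *Can an earlier FVC stand in?* No. A value before Day 324 maps to an earlier visit. A patient who dies after an in-window FVC keeps that value and is not affected.
4. *What remains?* The no-imputation default. SAP 5.1 points the same way, since categorical percentages use non-missing values.

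**Inputs for the size**

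- From the documents: placebo decline 200 mL (Protocol 2.1); difference 100 mL, SD 240 mL, N = 141, two-sided 10% level, 2:1 allocation (Protocol 14.6, SAP 3.1).
- The plan's own figure, 75% power for the primary endpoint, reproduces: 100 / (240 × √(1/47 + 1/94)) = 2.33; 2.33 − 1.645 = 0.69; Φ(0.69) ≈ 0.75. No power or response rate is given for the responder endpoint.
- Assumed: normal declines, predicted FVC of 3.0 to 4.0 L, the death rates, and no in-window FVC for any death (the upper bound). Baseline FVC is not adjusted for.

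**Formulas**

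Success among assessed patients is s = Φ((T − mean decline) / 240), with T equal to 10% of predicted FVC. For placebo, s = Φ(100/240) = 0.662 at 3.0 L and Φ(200/240) = 0.798 at 4.0 L. With deaths dropped, OR = odds(s on 3 mg) / odds(s on placebo). With deaths as failures, each s is replaced by p = s(1 − d), where d is the arm's death rate.

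**Equal success in both arms.** Dropping deaths always gives 1.00. For example, at 3.0 L with 5% and 2.5% deaths: p = 0.6285 (odds 1.692) and 0.6450 (odds 1.817), so OR = 0.93.

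| Assumed deaths, 3 mg / placebo | OR, deaths as failures, 3.0 L | 4.0 L |
|---|---|---|
| 5% / 2.5% | 0.93 | 0.89 |
| 2.5% / 5% | 1.07 | 1.12 |
| 10% / 5% | 0.87 | 0.81 |
| 5% / 10% | 1.15 | 1.23 |
| equal | 1.00 | 1.00 |

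If only half of the 5% / 2.5% deaths lack an in-window FVC, the figures are 0.96 and 0.94. For the ≤5% endpoint (s = 0.42 to 0.50), 5% / 2.5% gives 0.96 to 0.95 and 10% / 5% gives 0.92 to 0.90.

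**Design alternative (200 against 100 mL), 5% deaths in each arm**

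- 3.0 L: s = 0.798 and 0.662. Dropped: OR 2.02. As failures: p = 0.758 and 0.628, OR 1.85.
- 4.0 L: s = 0.894 and 0.798. Dropped: OR 2.15. As failures: p = 0.850 and 0.758, OR 1.81.

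So equal deaths do not remove the distortion when success differs.

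**Against sampling error.** The Primary Population mixes patients randomized 2:1 with patients randomized 1:1 between 3 mg and placebo, so the split lies between 94:47 and 70.5:70.5. The SE of the log odds ratio with deaths dropped is then about 0.36 to 0.46. With equal success, the shift is about 0.19 to 0.26 SE at 5% / 2.5% and 0.36 to 0.47 SE at 10% / 5%. About 5 to 6 patients leave the analysis in the first case and 11 to 12 in the second.

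**Constructed examples (94:47).** Survivor success of 64/85 on 3 mg and 27/45 on placebo gives OR 2.03, p = 0.073. Adding 9 and 2 deaths as failures (64/94 and 27/47) gives OR 1.58, p = 0.215. In the other direction, 67/89 and 26/40 gives p = 0.231, and adding 5 and 7 deaths (67/94 and 26/47) gives p = 0.061.

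**The case against.** No sentence says that deaths are excluded; the exclusion follows from reading several rules together. Loss to follow-up before Week 52 could be read loosely as not being followed to Week 52, which would make deaths failures. The intent-to-treat principle, the mITT set and the composite strategy for death in Protocol 14.8 suggest that this is what the authors would want. The blinded review meeting may adjudicate SAP definitions (SAP 4.6). The stakes are also limited: SAP section 5 calls efficacy p-values exploratory, there is no multiplicity adjustment (SAP 7.1.3), and death is tested separately whatever the event count (SAP 7.2.3.4).

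Most of this stands as a limit on importance. It does not close the gap. The loose reading conflicts with how both documents use the term, Protocol 14.8 is confined to the primary analysis, and the review meeting has no written rule to apply.

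A reader might infer that the sponsor chose a survivors-only analysis, or that the omission favours GB0139. The documents support neither. The text looks like incomplete drafting, and the direction depends on deaths and success rates that are not known.

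**Conclusion.** The point holds. As written, SAP 7.2.3.1, and 7.2.4.1 by reference, leave patients who die with no in-window % predicted FVC without an outcome. The odds ratio is unaffected only if both deaths and success are equal between arms.

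The sizes are illustrations. The documents give no trial death rate. The related figures are the protocol's 5% threshold for analysing time to death, which the SAP removed, and a general IPF median survival of 2 to 3 years from diagnosis (Protocol 4.1). Under a constant hazard the latter would mean 1 − 0.5^(1/3) = 21% to 1 − 0.5^(1/2) = 29% deaths a year. Enrolled patients may differ, since they may be up to five years from diagnosis and need FVC above 45% of predicted. Under the assumed rates the shift is a fraction of one standard error.

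A reader might conclude that the superiority result would change. The constructed examples show that it can at the 10% level, but they were chosen with uneven deaths and a result near the boundary. The primary endpoint has its own death rule and is not affected. The gap is worth closing because it concerns a key secondary superiority test and is cheap to settle before unblinding.

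**What to change.** Add to SAP 7.2.3.1, for the Primary Population:

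> Subjects who die before Week 52 with no % predicted FVC in the Week 52 window are counted as decline >10% (>5% for 7.2.4.1).

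The same gap exists in the SoC1 and SoC2 populations, in their 26-week versions (window Day 135 to 232), and for living subjects with no in-window value who are not lost to follow-up, such as those who withdraw or have a lung transplant. How to classify these is a judgement. A sensitivity analysis, for example multiple imputation by arm, is optional.

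The cost is one sentence before database lock and no new data. Responder proportions fall by s × d: for the ≤10% endpoint, about 1.7 to 2.0 percentage points in an arm with 2.5% such deaths and 3.3 to 4.0 points in an arm with 5%.

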#### 7.2.3.2 Change from baseline in St. George's Respiratory Questionnaire total score at Week 52.

Data from an external central vendor (Clario/ERT) with the SGRQ results will be used. The details of scoring are provided in Section 11.6.

A Mixed Model with Repeated Measures (MMRM) will be fitted to the change from baseline in the SGRQ Total Score across all visits (Weeks 12, 26 and 52 - see Section 11.2). Treatment, visit, baseline SGRQ Total Score, and treatment-by-visit interaction will be fitted as fixed effects. A restricted maximum likelihood (REML) approach will be used, and an unstructured covariance structure shared across treatment groups will be used to model the within-subject errors. If the model fails to converge, a heterogeneous Toeplitz structure (TYPE=TOEPH option in PROC MIXED rather than TYPE=UN) will be used. The Kenward-Roger's correction to degrees of freedom will be applied.

Domain scores will be summarized by treatment group and visit only.

	Plus-Project Statistical Analysis Plan	
	Protocol Number: GALACTIC-1	Version: 1

The analysis will be repeated by subgroup (separately for each subgroup factor of interest). A fixed effect for the subgroup factor will be added and all interaction terms between treatment, visit and the subgroup factor will be included. The comparisons between treatments at each visit will be assessed within each level of the subgroup.

### 7.2.3.3 Time to first hospitalization (respiratory related, including acute exacerbation of IPF)

The time to first hospitalization (respiratory related, including acute exacerbation of IPF) will be derived from the 'Exacerbation' and 'Adverse Events' eCRF.

If the subject was hospitalized and the AE linking to the hospitalization indicates that the PI/treating physician classed the AE as the result of an exacerbation of IPF then the hospitalization will be defined as being respiratory related, including acute exacerbation of IPF.

Other respiratory related causes will be defined as all AEs in the 'Respiratory, Thoracic and Mediastinal Disorders' System Organ Class (SOC), plus those AEs in the 'Infections and Infestations' SOC with preferred terms containing the character strings 'resp', 'bronch', 'covid-19' or 'pneumo', or the specific PTs as follows:

- Influenza
- Legionella infection
- Viral infection

If a subject was hospitalized (respiratory related, including acute exacerbation of IPF) prior to or on Day 379 (Week 52 plus 2 weeks) then the  $(\text{date of first such hospitalization} - \text{date of randomization} + 1) / 7$  will be derived as the time to first hospitalization (respiratory related, including acute exacerbation of IPF) in weeks.

If a subject does not require hospitalization (respiratory related, including acute exacerbation of IPF) prior to or on Day 379, they will be censored in the analysis. The following censoring rules will be applied:-

- If lost to follow-up (LTFU), a subject will be censored at the earliest of date of last contact and Day 379
- If a subject discontinued (and not lost to follow-up), they will be censored at the earlier of the date of study discontinuation and Day 379.
- Otherwise, censor at the earliest of last contact date or Day 379.

	Plus-Project Statistical Analysis Plan	
	Protocol Number: GALACTIC-1	Version: 1

The superiority of GB0139 3mg compared to Placebo will be tested for the time to first hospitalization (respiratory related, including acute exacerbation of IPF).

The null hypothesis is:

$H_0$  : There is no difference in the time to first hospitalization between GB0139 3mg and Plc

The alternative hypothesis is:

$H_a$ : There is a difference in the time to first hospitalization between GB0139 3mg and Plc

A Cox proportional hazards model will be fitted with treatment and baseline FVC (mL) included in the model. The Wald test will be used to test for differences between treatments. Hazard ratios together with 90% and 95% confidence intervals will be used to quantify the effect of treatment, comparing GB0139 3mg to Placebo as the reference. Breslow’s method for handling ties will be used.

The analysis will be repeated by subgroup (separately for each subgroup factor of interest) by adding a fixed effect for the subgroup factor and adding a treatment by subgroup interaction term. The hazard ratio between treatments will be assessed within each level of the subgroup.

If there are fewer than 15 events (respiratory related, including acute exacerbation of IPF) then a formal statistical analysis will not be performed, and only frequencies of hospitalizations by treatment group will be provided. If an overall analysis is performed, then the subgroup analyses will automatically be performed, regardless of the number of events in the subgroup levels.

Kaplan-Meier plots by treatment group will also be presented.

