18.3 Appendix 3. Definition of Acute Exacerbations in IPF

Acute respiratory worsening occurs in a small minority of patients with IPF annually (approximately 5–10%) [1-3]. These episodes may occur secondary to common conditions such as pneumonia, pulmonary embolism, pneumothorax, or cardiac failure [4]. When a cause cannot be identified for the acute respiratory decline, the term acute exacerbation of IPF has been used [3, 5-15]. It is presently unclear if acute exacerbation of IPF is simply a manifestation of an unidentified respiratory complication (such as pulmonary emboli, infection) contributing to an acute worsening in a patient with IPF or represents an inherent acceleration in the pathobiological processes involved in IPF.

Regarding the definition of AE in IPF, a revised "conceptual framework" was proposed by an international working group in 2016 [16].

The 2007 proposed definition of an "acute exacerbation" (AE) of IPF included all of the following:

- A previous or concurrent diagnosis of IPF
- Deterioration within 30 days
- New bilateral ground glass opacities and/or consolidation on a background of reticular or honeycomb pattern consistent with usual interstitial pneumonia (UIP)
- No evidence of pulmonary infection by endotracheal aspiration or bronchoalveolar lavage
- Exclusion of alternative causes including left heart failure, pulmonary embolism, or an identifiable cause of acute lung injury

The 2016 revised criteria more accurately reflect today's knowledge of AE-IPF and should allow for better insights into the etiology, treatment, and outcomes of this process [17]. Similar to the definition in 2007, this newly proposed framework defines an AE as "*an acute, clinically significant respiratory deterioration characterized by evidence of new widespread alveolar*

abnormality," but does not set an exact 30 day limit for symptom onset and does not require exclusion of infection. The following diagnostic criteria are proposed:

- A known diagnosis of IPF (diagnosis may be made at the time of acute respiratory deterioration)
- Acute worsening, "typically less than one month's duration"
- Computed tomography of the chest with new bilateral ground glass opacification and/or consolidation superimposed on a background of findings consistent with usual interstitial pneumonia (bibasilar reticular opacities associated with honeycomb changes and traction bronchiectasis)
- Heart failure or fluid overload does not fully explain the worsening.

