DIFFERENTIAL DIAGNOSIS — The differential diagnosis of AE-IPF includes venous thromboembolism, infection, and heart failure. A pneumothorax can complicate IPF, but would usually be recognized on a conventional chest radiograph. Pulmonary hypertension developing as a consequence of IPF is also in the differential diagnosis of worsening dyspnea, but would not have the new radiographic opacities associated with AE-IPF.

- **Venous thromboembolism** – IPF is associated with a significantly increased risk of venous thromboembolism (VTE) [40-42]. The suspicion for VTE is increased in patients with obesity, immobilization, malignancy, and prior or family history of VTE.
- **Infection** – For patients who can tolerate the procedure, our standard practice is to perform a full investigation for potential lung infection and to initiate empiric antibiotics for pneumonia while studies are pending, as described. The choice of antibiotics for community-acquired pneumonia is described separately.
- **Heart failure** – Given the average age of individuals with IPF, careful cardiac assessment for heart failure or myocardial infarction is appropriate. We typically begin with serial troponin, brain natriuretic peptide (BNP), and an electrocardiogram. An echocardiogram is not typically a first line assessment, but may be useful to evaluate for heart failure in a subset of patients, such as those with extrathoracic clinical features of heart failure or an elevated BNP.
- **Pulmonary hypertension** – Pulmonary hypertension (group 3), a well-known complication of IPF, also presents with worsening dyspnea, but without increased radiographic opacities. The diagnosis is often suspected in patients with worsening gas transfer without evidence of worsening interstitial lung disease. Plasma BNP is often increased, and Doppler echocardiography can provide an estimate of pulmonary artery systolic pressure. A firm diagnosis requires right heart catheterization.

References

1. King TE Jr, Behr J, Brown KK, du Bois RM, Lancaster L, de Andrade JA, Stahler G, Leconte I, Roux S, Raghu G. BUILD-1: a randomized, placebo-controlled trial of bosentan in idiopathic pulmonary fibrosis. *Am J Respir Crit Care Med* 2008;**177**:75–81.

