#### 7.2.4.9 Time to respiratory-related death

Respiratory related causes will be defined as in Section 7.2.3.3. The time to death due to respiratory related causes, in weeks, will be derived as (date of respiratory-related death – date of randomization +1)/7.

If a patient does not die due to respiratory related causes on or prior to Day 379, the same censoring rules will apply as in Section 7.2.3.3.

Cox proportional hazards modelling, as detailed in Section 7.2.3.3, will be performed.

	Plus-Project Statistical Analysis Plan	
	Protocol Number: GALACTIC-1	Version: 1

7.2.4.10 Change in FVC expressed in mL over 52 weeks for subjects who have never been treated with pirfenidone or nintedanib

The same data source and analyses (random coefficients regression model) as detailed in Section 7.2.1 will be used. Statistical analysis will be performed for the Primary Population and descriptive analyses only for the SoC2 / Monotherapy Population.

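### The infection part of the respiratory-hospitalisation definition can miss lung, pulmonary and pleural terms and can count infections at other body sites; a blinded term list should replace the string match

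*SAP*

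**What the plan says.** SAP 7.2.3.3 gives three routes by which a hospitalisation becomes an event for this key secondary endpoint.

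1. **Exacerbation flag.** The investigator or treating physician "classed the AE as the result of an exacerbation of IPF then the hospitalization will be defined as being respiratory related".
2. **Respiratory class.** "Other respiratory related causes will be defined as all AEs in the 'Respiratory, Thoracic and Mediastinal Disorders' System Organ Class (SOC"), with no filter on terms.
3. **Infection supplement.** Adverse events in the Infections and Infestations class "with preferred terms containing the character strings 'resp', 'bronch', 'covid-19' or 'pneumo", or with one of three listed preferred terms: Influenza, Legionella infection and "Viral infection".

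The SAP does not say whether matching ignores case. The section also sets a floor: "If there are fewer than 15 events (respiratory related, including acute exacerbation of IPF) then a formal statistical analysis will not be performed"; below it, frequencies by arm are reported. SAP 7.2.4.9 extends the definition to deaths: "Respiratory related causes will be defined as in Section 7.2.3.3".

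The protocol gives no operational definition of 'respiratory related', and its section 14.1 leaves the definition of analysis variables to the SAP. Protocol 12.2 makes event adjudication optional and places it after read-out. SAP 4.6 has the Blind Data Review Meeting settle SAP definitions before lock and unblinding, but names no review of hospitalisation or death terms.

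**The concern.** The third route decides by spelling. For an infection admission that is neither flagged as an exacerbation nor coded in the respiratory class, what counts is whether four letter sequences appear in the preferred term, not where the infection is. Chest infections can be described without any of the four. The protocol's Appendix 3 does so in its own prose ("perform a full investigation for potential lung infection"; "No evidence of pulmonary infection by endotracheal aspiration or bronchoalveolar lavage"), although that is clinical text and not coded data. Conversely, one listed term carries no body site, and 'pneumo' also matches the name of an organism that can infect sites other than the lung.

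At stake are the event count of a key secondary endpoint, whether that endpoint is formally tested at all, and the cause assigned to some deaths in another secondary endpoint. If a gap is found after unblinding, repairing it is a post hoc change.

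**Working it through.** **The plan's own figures.** No hospitalisation rate, expected event count, hazard ratio or power is given for this endpoint. The only sizing for the current design is for FVC: 100/(240·√(1/94 + 1/47)) = 2.332, and Φ(2.332 − 1.645) = 75.4%, which agrees with the stated 75% for 141 subjects. It has no bearing on this endpoint.

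**String test.** The infection supplement was applied to example wordings. These test the logic only. They are not known to be coded terms in this trial.

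| Wording | Counted, case ignored | Counted, case respected |
|---|---|---|
| lung infection, lung abscess | no | no |
| pulmonary infection, pulmonary sepsis | no | no |
| pleural infection | no | no |
| H1N1 influenza | no | no |
| Pneumonia, Bronchitis, Respiratory tract infection, COVID-19 | yes | no |
| Influenza, Legionella infection | yes | yes |
| Viral infection (any site) | yes | yes |
| pneumococcal bacteraemia, meningitis pneumococcal | yes | yes |

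The last column shows why case handling needs stating: read literally, the lower-case strings fail on the commonest capitalised terms.

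**Effect on the 15-event floor.** At 15 true events one lost event cancels the formal test; at 16 it takes two, and at 20 it takes six. For a range, assume a Poisson count with expected value 14, 17 or 20 and a missed share of 0, 5 or 10%, and compute P(count ≤ 14):

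| Expected events | None missed | 5% missed | 10% missed |
|---|---|---|---|
| 14 | 57% | 64% | 72% |
| 17 | 28% | 35% | 44% |
| 20 | 10% | 15% | 21% |

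Both the expected counts and the missed shares are assumptions. The table counts losses only. Wrongly counted events would partly offset them, and a missed first admission removes a subject's event only if no later qualifying admission follows by Day 379.

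**Effect on power.** Schoenfeld's formula with 2:1 allocation and two-sided 10% gives power = Φ(√(D·(2/3)·(1/3))·|ln HR| − 1.645). Assume a true hazard ratio of 0.5.

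- D = 20: √(20·2/9)·0.693 = 1.461, so power is 42.7%.
- 10% missed at the same rate in both arms: D = 18, hazard ratio still 0.5, power 39.8%.
- In addition, 5% of counted events unrelated to treatment: D = 18/0.95 ≈ 18.9, observed hazard ratio about 0.5·0.95 + 1·0.05 = 0.525, power 37.3%.
- The same three steps from D = 30 give 55.8%, 52.1% and 49.0%.

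The two errors therefore act differently. Missed events at equal rates cost precision but leave the hazard ratio where it was. Wrongly counted events pull it towards 1.

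**The case against.** The strongest reply is that this is a narrow drafting gap with no demonstrated effect. Most of that reply stands.

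- **Scope.** A reader might infer that respiratory hospitalisations as a whole are found by four strings. They are not. The strings work only inside the infection supplement, and the exacerbation flag can recover an infection that the strings miss.
- **Occurrence.** A reader might infer that events are in fact miscounted. Nothing shows this. There is no adverse-event listing and no coding dictionary to confirm that the example wordings are preferred terms, which class they fall in, or that any occurred. The named terms would fit a list built from blinded coded data, in which case few or none would be missed. The SAP does not say that it was built this way.
- **Conflict with the protocol.** The protocol refers to any respiratory-related hospitalisation, and a reader might see the SAP rule as a departure. As the protocol delegates variable definitions to the SAP, this is not a contradiction.
- **Consequence.** Below the floor, frequencies are still reported, and Kaplan-Meier plots are planned. Power is only about 35% at 15 events even with an assumed hazard ratio of 0.5. SAP 5 describes efficacy p-values as exploratory. All-cause hospitalisation and all-cause death do not use the rule, and respiratory death is not a key secondary endpoint.

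The logic of the rule itself is not answered. It excludes terms that name the lung or pleura and includes terms that name no respiratory site. The planned data review could catch this, but nothing instructs it to look.

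**Conclusion.** The concern holds as a weakness of the infection supplement: for admissions outside the exacerbation flag and the respiratory class, the rule can both miss and wrongly add events, and the same applies to respiratory-related death. The size in this trial is unknown and may be zero.

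On the assumptions shown, a 5–10% loss raises the chance of missing the 15-event floor by about 5 to 15 percentage points. Adding 5% unrelated events to a 10% loss takes power at 20 events from 42.7% to 37.3%. Because both arms are classified by one rule under blinding, no directional bias is expected unless the drug changes the frequency of the infections concerned. This is a modest point, worth correcting because the correction is cheap and must come before unblinding to remain pre-specified.

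**What to change.** Before lock and unblinding, have the Blind Data Review Meeting classify every preferred term linked to a hospitalisation or death, in any class, as respiratory yes or no, blinded to treatment. Record the result as a fixed list and use it for SAP 7.2.3.3 and 7.2.4.9 in place of the string match. 'Viral infection' carries no site, so a term-level answer cannot settle it: count such an event only when the blinded review classifies that event as respiratory.

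If strings are kept as a first screen, state that matching ignores case and add 'lung', 'pulmon' and 'pleur'. Do not add 'influenza' as a bare substring. It would also match terms containing 'influenzae' at any site, the same fault as 'pneumo' with 'pneumococcal'.

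The cost is a paragraph of SAP text and a short blinded medical review of a small list, at a meeting already planned.
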